**Studies at baseline:**

1. History and Physical exam
2. Baseline weight and height

*Head and Neck:*

- Neuro-psychiatric evaluation at baseline (+/- 6 months) if >20% of the whole brain received 10% of the prescribed dose as determined by the radiation oncologist evaluating the treatment plan.
- Baseline panel of endocrine labs recommended within 6 weeks of the radiation start date if the dose to the pituitary or hypothalamus received 20 Gy RBE or more, or if the whole thyroid was included in the radiation port. Labs include TSH, Free T4, Cortisol (AM value), IGF-1, IGF-BP3, LH, FSH, prolactin, estradiol (females) or testosterone (males).
- For patients who received any dose to oral structures (as deemed necessary by the PI) a routine dental evaluation is recommended to screen for any major dental deficiencies.

*Orbit:*

- Baseline ophthalmologic exam to be completed (+/- 6 months) if the orbit is in the involved field.

*Ear or middle ear involvement (Performed within the first three weeks of treatment):*

Audiometric exams with word recognition must be completed up to 6 weeks before or within 10 weeks after the start of radiation if the mean radiation dose to the cochlea received 20 Gy RBE or more, or for patients in which the tumor involved one or both of the 8th cranial nerves. The word recognition portion of the exam will be administered to age and developmentally appropriate children, generally age 4 and over.

**Criteria for Removal from Study:**

If a patient develops recurrent disease, he/she will be taken off treatment and followed per standard of care. All patients will continue to be followed for survival status.

**Acute Toxicity:**

Acute toxicity will be scored at weekly status check visits by the radiation oncology nurse or doctor. In addition, acute toxicity will be scored at least one time within the 3 months following completion of radiation therapy. This may be scored by the local pediatric oncologist if the patient does not return to the treating institution for a follow-up visit during this time frame. The recommended evaluation time for acute toxicity after radiotherapy is 6 weeks following completion, but may be at any time during the 3 months after treatment. In addition, any event requiring admission must be recorded. Acute toxicities will be graded according to the Common Terminology Criteria for Adverse Events (CTCAE), Version 3.0.

All toxicities and adverse events that are possibly, probably or definitely related to radiation therapy will be captured on the case report forms.

**Late toxicity (Site specific):**

Late toxicity is to be scored on a yearly follow-up basis for at least five years. Ten years is suggested but not required. Additional tests may be required as clinically indicated. Late toxicities will be graded according to the Common Terminology Criteria for Adverse Events (CTCAE), Version 3.0.

*General studies at yearly follow-up visits:*

1. History and Physical exam
2. Weight and height

*Head and Neck:*

- Neuro-psychiatric evaluation every other year (+/- 12 months) if >20% of the whole brain received 10% of the prescribed dose as determined by the radiation oncologist evaluating the treatment plan.
- Endocrine labs recommended to be drawn annually if the dose to the pituitary or hypothalamus received 20 Gy RBE or more, or if the whole thyroid was included in the radiation port. Labs include TSH, Free T4, Cortisol (AM value), IGF-1, IGF-BP3, LH, FSH, prolactin, estradiol (females) or testosterone (males).

*Orbit:*

- Annual ophthalmologic exam to be completed (+/- 6 months) if the orbit is in the involved field.

*Ear or middle ear involvement*

Annual audiometric exams with word recognition must be completed (+/- 6 months) if the mean radiation dose to the cochlea received 20 Gy RBE or more, or in patients in which the tumor involved one or both of the 8th cranial nerves. The word recognition portion of the exam will be administered to age and developmentally appropriate children, generally age 4 and over.

**Comparison of Proton Plans and Photon Plans:**

Normal structures will be contoured on treatment planning CT scan in the treatment planning systems. Dose volume histograms will be generated and compared for important normal structures as well as tumor targets that will receive dose and likely contribute to either acute or late morbidities. DVH levels at 90%, 50%, and 10% will be compared between the two plans. A mean average percent of total dose prescribed will be calculated based on the three DVH levels for each normal structure at risk for both proton and photon plans. The percent of normal tissue spared by using protons will be calculated by using the following equation.

$$\frac{(\text{mean X-ray dose} - \text{mean proton dose})}{\text{mean X-Ray dose}}$$

The treatment volume will be contoured by the treating physician and the normal structures will be contoured by the treating physician, study physician, the dosimetrist, or the anatomist depending on the difficulty of the structure to be outlined.

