## **II. SPECIFIC AIMS (RESEARCH OBJECTIVES)**

1. To assess late complications from irradiation using proton beam therapy in place of conventional photon beam therapy in pediatric patients with rhabdomyosarcomas.
2. To assess acute side effects from irradiation using proton beam therapy in place of conventional photon beam therapy in pediatric patients with rhabdomyosarcomas.
3. To compare the dose distribution to tumor and surrounding normal structures using DVH's (Dose Volume Histograms) generated from the proton plan used to treat the patient and the photon plan generated for comparison purposes. Photon plans for comparison purposes will be completed for the first 79 patients.
4. To monitor the rates of event-free survival, overall survival and local control using proton radiotherapy.

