### **Target delineation:**

The following structures will be outlined on planning CT scans. It is recommended that the radiation oncologist outline the GTV. Cumulative dose volume histogram analysis will be completed for structures marked \*:

- \* GTV and surgical bed
- \* CTV

At least 4 normal organs receiving any radiation will be drawn to delineate dose these receive. Organs will be site specific and left to the discretion of the treating physician

Suggestion of critical organs to track include:

- Head and neck organs: retinas, lens, bony orbit, pituitary gland, hypothalamus, whole brain, temporal lobe, Mandible, cochlea, larynx, orbit, thyroid gland, esophagus, spinal cord
- Thorax: Lung, Heart, left ventricle, bone, esophagus, spinal cord, nerves
- Abdomen: liver, kidney, stomach, spleen, bone spinal cord, small bowel
- Pelvis: testis, ovaries, small bowel, bladder, rectum
- Extremities: growth plate, nerve, vascular structures

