### **Field Arrangements and Treatment Planning:**

An optimized 3-D conformal proton plan will be designed in consultation with the treating physician. Whenever possible multiple fields will be designed to limit the dose to normal tissues and critical structures and promote symmetric bone growth/retardation where applicable.

An optimized IMRT comparison photon plan will also be generated for the first 79 patients. Appropriate measures such as cerrobend blocks or MLCs will be fabricated or programmed so that the patient can be treated with photons in the event of an equipment malfunction rendering proton therapy unavailable. A patient may receive up to 25% of the prescription dose with photons provided the normal tissue tolerance limits are respected. In addition, this photon plan will serve as a comparison of doses to normal surrounding organs in the form of Dose Volume Histograms. A comparison of normal tissue doses will be made between the two plans as a primary objective of this study.

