## **VI. BIOSTATISTICAL ANALYSIS**

Primary outcomes are acute and late complications following proton beam irradiation to the tumor or tumor bed. Late complications are defined as the delayed effects attributable to radiation which occur > 90 days following completion of radiation, while acute side effects are those occurring during radiotherapy or up to 90 days after the last dose. Allowing for 5% inflation for unevaluable patients due to ineligibility or early dropout, the revised accrual goal is a total of 115 patients with a minimum follow-up of another 2

years following the patient enrollment for observing the late complications of proton beam irradiation.

The goal of utilizing protons is an improvement in the historical complication rate, which varies by site and type of complication. The literature for parameningeal or other head and neck rhabdomyosarcomas has reported endocrine effects occurring in 50-100% and impaired orbital function in 70-100% of patients (23-27). For children treated for pelvic tumors, late effects were significantly higher among patients treated, ranging from 54% to 77% (28). Across all anatomic sites, the likelihood of one or more reported late effects has been approximately 70% or more among those who received conventional radiation. Among a total of 110 patients, the probability is 81% that 70 or fewer of them will develop any late effect if the overall complication rate is truly decreased to 60% with the use of protons. The decision rule is associated with only 9% probability if the underlying rate were truly similar to the 70% historical rate observed with conventional radiation.

Due to a difference in the radiation doses used for treating patients with different tumor characteristics (typical doses are 36 Gy, 41.4 Gy, 45 Gy and 50.4 Gy), the outcomes will be analyzed according to dose group,  $\leq$  45 Gy and  $\geq$  45 Gy. Data on the enrolled patients shows a 1:4 ratio in the distribution of patients receiving low versus intermediate radiation doses. Constitutional symptoms, namely fatigue and malaise, as well as skin reactions in the radiation port will be analyzed according to dose group.

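### The mean dose in the proton-versus-photon sparing ratio is an average of three DVH levels, which is not the mean dose and can misstate sparing in partly irradiated organs

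*Combined protocol and SAP*

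**What the plan says.** Section IV, *Comparison of Proton Plans and Photon Plans*, sets out three steps.

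- Reading the curves: "DVH levels at 90%, 50%, and 10% will be compared between the two plans".
- Summarising each organ: "A mean average percent of total dose prescribed will be calculated based on the three DVH levels for each normal structure at risk", separately for the proton and the photon plan. No weights are given.
- Forming the ratio: "The percent of normal tissue spared by using protons will be calculated by using the following equation". The equation is mean X-ray dose minus mean proton dose, divided by mean X-ray dose.

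No other definition of mean dose is given for this comparison. The text does not say whether the levels are volume levels (the dose reaching 90%, 50% or 10% of the organ) or dose levels (the volume receiving 90%, 50% or 10% of the prescription). It has no rule for a zero or very small photon value.

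On which organs enter, Section V, *Target delineation*, says: "At least 4 normal organs receiving any radiation will be drawn to delineate dose these receive". It sets no minimum irradiated volume, and the suggested structures include large ones, for example "Thorax: Lung, Heart, left ventricle, bone, esophagus, spinal cord, nerves".

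On status, Section II (Aim 3) says: "Photon plans for comparison purposes will be completed for the first 79 patients". Section V, *Field Arrangements and Treatment Planning*, adds: "A comparison of normal tissue doses will be made between the two plans as a primary objective of this study". Section VI does not list the comparison: "Primary outcomes are acute and late complications following proton beam irradiation to the tumor or tumor bed". It gives no analysis of the DVH data.

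**The concern.** The ratio is worded in terms of mean dose, and a reader of the results will take it as the relative reduction in mean organ dose. The plan's construction gives something else. Three points carry no information about dose between them, and none about dose confined to less than 10% of the volume. In a partly irradiated organ, a small change in irradiated volume near 10%, 50% or 90% can move the summary by up to a third of the full dose. The error depends on the shape of the curve. If the proton and photon curves for an organ differ in shape, it does not cancel in the ratio.

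At stake is the only summary statistic that the protocol defines for Aim 3. It could show large sparing where there is little, or none where there is much, and organs could be ranked wrongly against each other.

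**Working it through.** **Inputs.** From the protocol: the three levels, the unweighted average and the ratio. Every DVH shape below is assumed, because the documents show none. The plan states no sparing figure, so there is none to reproduce.

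**Formulas.** Doses are in percent of prescription. The unit in Section IV points to volume levels, so let D90, D50 and D10 be the doses reaching at least 90%, 50% and 10% of the organ.

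- Plan's mean = (D90 + D50 + D10)/3
- True mean = dose averaged over the whole volume, that is, the integral of the DVH
- Sparing = (photon − proton)/photon

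**Step-shaped DVHs**

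| Photon plan | Proton plan | True means | True sparing | Plan's means | Plan's sparing | Shift, points |
|---|---|---|---|---|---|---|
| 40% of organ at 100, rest 0 | 15% at 100, rest 0 | 40.0, 15.0 | 62.5% | 33.3, 33.3 | 0% | −63 |
| 30% at 100, 70% at 20 | 12% at 100, rest 0 | 44.0, 12.0 | 72.7% | 46.7, 33.3 | 28.6% | −44 |
| 8% at 100, 92% at 20 | 8% at 100, rest 0 | 26.4, 8.0 | 69.7% | 20.0, 0 | 100% | +30 |
| 55% at 100, rest 0 | 45% at 100, rest 0 | 55.0, 45.0 | 18.2% | 66.7, 33.3 | 50.0% | +32 |
| 9% at 100, rest 0 | 4% at 100, rest 0 | 9.0, 4.0 | 55.6% | 0, 0 | 0/0 | – |

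In the first row, both plans have D90 = 0, D50 = 0 and D10 = 100, so both summaries are 100/3 = 33.3 and the ratio is 0. The true value is (40 − 15)/40 = 62.5%.

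**Steep smooth DVHs.** Take D(v) = 100/(1 + exp((v − v0)/s)), where v is the volume fraction, v0 sets the irradiated fraction and a small s makes the fall steep. The true mean is 100·s·[ln(1 + exp(v0/s)) − ln(1 + exp((v0 − 1)/s))]. Shifts are from unrounded values.

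| Photon v0, s | Proton v0, s | True sparing | Plan's sparing | Shift, points |
|---|---|---|---|---|
| 0.42, 0.10 | 0.12, 0.02 | 71.5% | 42.8% | −28.7 |
| 0.42, 0.10 | 0.12, 0.05 | 70.5% | 53.2% | −17.3 |
| 0.42, 0.10 | 0.12, 0.10 | 65.3% | 55.3% | −10.0 |
| 0.42, 0.10 | 0.20, 0.02 | 52.5% | 22.3% | −30.2 |
| 0.42, 0.10 | 0.08, 0.02 | 80.9% | 79.0% | −1.9 |
| 0.30, 0.10 | 0.20, 0.02 | 34.4% | 0.9% | −33.5 |
| 0.30, 0.10 | 0.20, 0.10 | 30.2% | 22.3% | −8.0 |
| 0.40, 0.02 | 0.15, 0.02 | 62.5% | 8.2% | −54.3 |

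In the first row, the photon levels 0.8, 31.0 and 96.1 average 42.6 (true mean 42.1), so the photon summary is nearly right. The proton levels 0, 0 and 73.1 average 24.4 (true mean 12.0), so the proton summary is double the truth.

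**Broad smooth DVHs.** With beta-shaped dose distributions, Beta(5,5) for photon and Beta(3,7) for proton give 40.0% true against 39.6%. Beta(2,3) and Beta(1,4) give 50.0% against 48.4%. A strongly skewed pair, Beta(2,8) and Beta(0.1,0.9), gives 50.0% against 35.0%.

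A survey drew 10,000 beta pairs with photon mean 15% to 70%, proton mean 10% to 95% of the photon mean, and the sum of the two beta parameters between 0.7 and 10. The median absolute error was 2.6 points, the 95th percentile 11.9 and the 99th 18.1; 8% of pairs exceeded 10 points and 0.6% exceeded 20. With the parameter sum between 2 and 20 (less skewed), the median was 1.0 and the 95th percentile 4.7.

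**If the levels are dose levels.** The average is then a percent of volume, not a dose. Suppose 8% of the organ is at 100 in both plans and the rest is at 12 (photon) or 9 (proton). The true means are 8 + 0.92 × 12 = 19.04 and 8 + 0.92 × 9 = 16.28, so true sparing is 14.5%. The volumes are 8, 8 and 100 (average 38.7) for photon and 8, 8 and 8 (average 8) for proton, so the ratio gives 79.3%.

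**The case against.** The best defence is that the composite is openly defined, applied identically to both plans, and close to the mean for many curves. For a DVH that is logistic in dose, and hence symmetric, it agrees with the true mean to within about 0.2 points. The large shifts need a steep fall just beside a reading point: widening the proton curve in the smooth table from s = 0.02 to 0.10 cuts the shift from 29 to 10 points in one case and from 34 to 8 in another. The three levels are also to be compared in their own right, so the ratio is not the only output. All of this stands, and it limits the size of the error. It does not make the average a mean dose.

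A reader might infer that errors of tens of points are typical. The documents show no organ DVH, and the broad smooth curves point to a few points.

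A reader might also infer that the ratio will often be undefined. That needs zero photon dose at all three levels. The comparator is IMRT, Section I says that IMRT still has entrance and exit dose, and Section IV directs the comparison at structures that receive dose and matter for morbidity. A very small and therefore unstable denominator is the more realistic problem. Integral means share it, so changing the mean does not fully remove it.

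Nor do the documents establish that proton curves are always the worse affected. Section I supports the absence of exit dose but describes no organ DVH shapes.

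**Conclusion.** The point holds as a defect of definition with a cheap remedy. Followed as written, Section IV gives a sparing percentage that is not based on mean dose, and nothing elsewhere in the protocol overrides it. The error can go either way and depends on the organ. Under the assumed shapes it is usually a few points for broad smooth DVHs (median about 1 to 3, 95th percentile about 4 to 12), about 8 to just over 30 for most steep smooth curves, a little over 50 when both are nearly vertical, and 30 to 63 for the step examples with a defined ratio. Which of these applies to the trial's organs cannot be told from the documents.

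The consequence is confined to Aim 3 and to the comparison that Section V calls a primary objective. It would be wrong to read it as a threat to the trial's conclusion on complications: no test, threshold or sample size uses the sparing figure, and the rule of 70 or fewer late effects among 110 patients is untouched.

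**What to change.** In Section IV, *Comparison of Proton Plans and Photon Plans*:

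1. Define mean X-ray dose and mean proton dose as the mean structure dose integrated over the full DVH of each plan.
2. Keep the 90%, 50% and 10% levels as separate descriptive comparisons, and state whether they are volume or dose levels.
3. Report the absolute difference in mean dose alongside the ratio where the photon mean is near zero.

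The cost is a few sentences. The full DVHs are already generated for both plans, so no new contouring, planning or patient contact is needed, and plans already made can be summarised again. The protocol already relies on a mean structure dose elsewhere: mean cochlear dose is one trigger for audiometry at baseline and follow-up.

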## V. RADIATION THERAPY

National protocols: For those patients who are treated on a national protocol such as a COG protocol, the COG radiation therapy guidelines will be used.

### **Treatment Volume Parameters:**

For those patients who are not treated on a national protocol the ICRU 50 recommended terminology will be used to define the radiation treatment parameters. The definitions of clinical tumor volume (CTV) will vary according to the tumor location and disease characteristics and is delineated in detail by the IRS V protocols.

The GTV corresponds to the gross tumor visualized on MRI and CT scan images either after biopsy or resection. The CTV corresponds to the GTV plus the area that is likely to be microscopically involved with tumor.

The planning target volume (PTV) is defined as the clinical target volume plus a 2 to 20 mm margin for allowances in set-up uncertainties. A range is specified because the different parts of the body require more for set up uncertainty. For example, an intra-thoracic tumor can move as a result of breathing whereas a tumor in the orbit is less subject to normal physiologic motion once a patient has been appropriately immobilized.

### **Timing of the radiation therapy**

1. The clinical situation dictates whether the tumor or tumor bed will be irradiated pre-operatively, post-operatively or definitively without a gross total resection. Each case will be decided on its own merits according to guidelines listed in the national protocols for rhabdomyosarcoma or by the recommendations of the treating physicians (i.e. radiation oncologist, pediatric oncologist and surgical oncologist primarily.)
2. If a patient is treated post-operatively, the radiation treatments should begin within 35 days of the final surgery but delays up to 45 days will be allowed. Sarcoma surgery often requires reconstructive surgery that requires additional wound healing time.

### **Patient Set-up and Immobilization:**

Patient set-up and immobilization will be determined prior to obtaining the planning CT scan. The type of immobilization will be determined by the anatomic location of the site to be treated. For example, if the area to be treated is in the head and neck location, the head will be positioned such that the spinal cord will be as straight as possible, a head cup is often used in conjunction with a custom made aquaplast mask. If an extremity is to be treated, a custom immobilization device will be constructed to hold the area in the required position. An alpha cradle may be used to immobilize the trunk of the body as well. The immobilization device must be documented in writing in the patient care chart and by photograph.

### **Patient sedation:**

Patient set-up reproducibility is critical for both conventional radiotherapy and proton radiotherapy and the use of sedation or anesthesia is strongly encouraged if necessary. An anesthesiologist will be supervising and administrating sedation. Sedated patients should be under constant surveillance during treatments with cameras, telemetry, and other devices. The need for anesthesia is not modality dependent. A child requiring sedation for photon therapy would require it for proton radiotherapy and vice versa.

### **CT simulation:**

Patient undergoes a planning CT scan while in treatment position and properly immobilized. IV contrast is suggested but not required. In patients at risk for allergic reaction to contrast despite pre-medication, a planning CT scan may be obtained without contrast. Physicians are encouraged to use available MRI scans to aid in target and normal tissue delineation. Fusion of the MRI scans to the planning CT scans can help delineate structures. CT slices (generally 2 to 3.7 mm thick) are obtained through tumor bed and region and will include the full organs for which dose will be tracked.

Scans are sent to computer planning software. Adjustments in distance between slices can be made to accommodate the maximum number of slices at the discretion of the radiation oncologist and treatment planners.

### **Target delineation:**

The following structures will be outlined on planning CT scans. It is recommended that the radiation oncologist outline the GTV. Cumulative dose volume histogram analysis will be completed for structures marked \*:

- \* GTV and surgical bed
- \* CTV

At least 4 normal organs receiving any radiation will be drawn to delineate dose these receive. Organs will be site specific and left to the discretion of the treating physician

Suggestion of critical organs to track include:

- Head and neck organs: retinas, lens, bony orbit, pituitary gland, hypothalamus, whole brain, temporal lobe, Mandible, cochlea, larynx, orbit, thyroid gland, esophagus, spinal cord
- Thorax: Lung, Heart, left ventricle, bone, esophagus, spinal cord, nerves
- Abdomen: liver, kidney, stomach, spleen, bone spinal cord, small bowel
- Pelvis: testis, ovaries, small bowel, bladder, rectum
- Extremities: growth plate, nerve, vascular structures

